A drug product formulation of rHuPH20 (HYLENEX) obtained FDA approval on 2 December 2005. The approval indication is an adjuvant to increase absorption and dispersion of other injected drugs; for subcutaneous fluid administration; and as an adjunct in subcutaneous urography for improving resorption of radiopaque agents. HYLENEX was made available as saleable product beginning October 2006 and as of 31 December 2008 a total of 7,284 vials of HYLENEX had been sold. HYLENEX was made available through a product sampling program beginning June 2006, and as of 31 December 2008 a total of 4,384 vials had been received at physician offices. Thus, cumulative patient exposure from marketed HYLENEX product outside of clinical studies could be a high as 11,668 based on the total vials of saleable product and sample product distributed and the unit dose of 150 Units per treated patient.

Across 19 studies, a total of 525 study subjects had been enrolled as of December 31, 2008 among whom 510 subjects are known to have been exposed to at least one dose of HYLENEX/rHuPH20. Of the 510 subjects exposed to HYLENEX/rHuPH20 in clinical studies, 100 received an intradermal injection of a test dose of 15 Units of HYLENEX and 410 subjects received a subcutaneous (SC) injection of HYLENEX/rHuPH20 either immediately before or admixed with a co-injected drug or fluid administration. [Table 1](#) shows the cumulative number of subjects known to have been exposed according to the dose of HYLENEX/rHuPH20. There have been six studies to date in which at least some study subjects are known to have received more than a single exposure to HYLENEX: HZ2-07-03 (two doses per subject), 1838-003 (more than one dose permitted), HZ2-07-02 (a two-part study with some subjects participating in both parts), HZ2-07-04 (up to four doses per subject), HZ2-08-04 (up to six doses per subject) HZ2-08-05 (up to five doses). [Table 1](#) presents the completed HYLENEX/rHuPH20 clinical studies.

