### 3. STUDY DESIGN

#### 3.1. Overview of Study Design

This is a pilot Phase II, prospective, double-blind, placebo-controlled study to compare the efficacy, safety and tolerability of rHuPH20 or placebo control administered intradermally (ID) in the prevention and treatment of subjects with contact allergy to nickel. This study will involve two treatment regimens, which will run in parallel (Treatment Regimens 1 and 2). A maximum of 30 subjects will be enrolled to achieve a likely estimate of 20 evaluable adult subjects. This study will be conducted at a dermatology unit.

Subjects with a known history of contact allergy to nickel will be recruited for the Screening period. During the Screening period, subjects will be tested to confirm the presence of cutaneous nickel sensitivity using the 1, 2.5, and 5% nickel sulfate patch. The concentration of nickel sulfate for each subject that causes no greater than a ++ cutaneous reaction (2 out of 4), International Contact Dermatitis Research Group [ICDRG] scoring scale will be the concentration administered at Baseline.

After re-confirmation of the subject meeting all inclusion/exclusion criteria and prior to dosing, each subject will have the upper half of the posterior aspect of the torso divided into two equal spaces using a template and marking the edges with a medical marking pen.

There will be two treatment regimens in this study (1 and 2), which will be conducted in parallel. Within each regimen, the four patch areas will be randomized to rHuPH20 or placebo control for each subject. The randomization for Treatment Regimen 1 will be independent of the randomization for Treatment Regimen 2; thus, two randomization schemes (one for each Treatment Regimen) will be used. Specifically, for each subject, two random patch areas in Treatment Regimen 1 will be assigned rHuPH20; the other two patch areas in Treatment Regimen 1 will receive Placebo control. This same randomization concept will be used in Treatment Regimen 2.

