### Dataset for Analysis

The primary analysis data set for this study will consist of all evaluable subjects. An evaluable subject is one who has completed dosing (or prematurely discontinued the administration due to a toxicity) and has undergone sufficient assessments to allow an assessment of the tolerability of the administration. A secondary analysis data set will consist of all intent-to treat subjects (ITT) (i.e., all subjects enrolled, defined as subjects assigned a subject identification number at the time of study enrollment in anticipation of receiving a dose of study drug). The safety analysis data set is all subjects exposed to rHuPH20 or placebo control.

The hypothesis is that 1) pre-treatment of rHuPH20 prior to nickel allergy testing will decrease the severity of the allergic skin reaction as compared to placebo control and 2) rHuPH20 will decrease the severity of nickel contact dermatitis as compared to control. The null hypothesis for this study is that rHuPH20 will not be different than what will be observed from placebo control. The alternative hypothesis is that rHuPH20 will be better than placebo control.

The sample size of 20 evaluable subjects is intended to provide a sufficient sample size to allow for a meaningful comparison between rHuPH20 and placebo control.

All data collected, including demographics, baseline information, contact dermatitis scoring, safety data, will be summarized by treatment group. Descriptive statistics including the number of observations (N), mean, standard deviation, median, and range will be presented for the continuous variables. Frequency and percentage will be presented for categorical variables. Figures of the individual measurements over time by subject and means by treatment group may also be provided.

Descriptive statistics will be used to summarize all efficacy variables. No formal statistical comparisons between treatments are planned.

All safety data will be examined, including AEs, physical examination findings, and vital signs. The incidence of subjects with AEs will be tabulated by MedDRA System Organ Class (SOC) and Preferred Term, seriousness, severity grade, relatedness to study drug, and localization to infusion site. Descriptive statistics will be used to summarize all safety variables.

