9. STUDY ANALYSIS

The hypothesis for this study is that 1) pre-treatment or rHuPH20 prior to nickel allergy testing will decrease the severity of the allergic skin reaction as compared to placebo control and 2) rHuPH20 will decrease the severity of nickel contact dermatitis as compared to control. The null hypothesis is that rHuPH20 will not be different than what will be observed from placebo control.

Figures, listings and descriptive statistics will be used to summarize all efficacy variables. No formal statistical comparisons between treatments are planned.

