9.1 Statistical Analyses

The primary analysis is the pair-wise intra-subject comparison of endpoint parameters for the injections with and without rHuPH20. The secondary analysis covers safety and other endpoint parameters (see Section 10).

ICDRG scores will be shown for Treatment Regimen 1 and Treatment Regimen 2 by injection types (rHuPH20 or Placebo) at Baseline, Day 4, Day 5, Day 6, Day 7 and Day 14. ICDRG scores will be reported by subject using figures (Figure 1) and listings (Listing 8).

A qualitative medical review of the ICDRG scores will be used to investigate:

- Possible treatment effect of rHuPH20 or placebo control injection on the exposure to topical nickel allergen.
- Proportion of subjects that have a ≥ 1 grade reduction in at least one patch region.

At the conclusion of the study, findings from the medical review will be summarized in the clinical study report.

For Treatment Regimen 2, the day of maximal ICDRG Score will be used to assess the possible effect each injection type has on the onset of reaction to topical nickel allergen. The day of maximal ICDRG Score will be summarized for each injection type using counts and percentages (Table 6.1/6.2). Possible days of maximal ICDRG Score include

the following: Day 4, Day 5, Day 6, Day 7, and Day 14. If the maximal ICDRG Score for an injection type occurred prior to treatment, the subject will be reported as never having had an ICDRG Score more severe than Day 3 for summary purposes.

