11. SAMPLE SIZE CALCULATION

The sample size of 20 evaluable subjects is intended to provide a sufficient sample size to allow for a meaningful comparison between rHuPH20 and placebo control.

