Laboratory Parameter	ITT (N=)	Safety (N=)	Evaluable (N=)
WBC (X 1000/uL)			
N	n	n	n
Mean (SD)	xx.x (xx.xx)	xx.x (xx.xx)	xx.x (xx.xx)
Median	xx.x	xx.x	xx.x
Min, Max	xx, xx	xx, xx	xx, xx
RBC (X Mil/uL)			
N	n	n	n
Mean (SD)	xx.x (xx.xx)	xx.x (xx.xx)	xx.x (xx.xx)
Median	xx.x	xx.x	xx.x
Min, Max	xx, xx	xx, xx	xx, xx
..			

path\t_program.sas date time

Programmer note: Table will include the following hematology parameters: Hemoglobin (g/dL), Hematocrit (%), Platelets (X 1000/uL), Neutrophils (segs) (%), Neutrophils (bands) (%), Lymphocytes (%), Monocytes (%), Eosinophils (%) and Basophils (%).

Table
Incidence of Clinically Significant Laboratory Abnormalities at Screening
All Subjects

Any Clinically Significant Abnormalities?	ITT (N=)	Safety (N=)	Evaluable (N=)
WBC	n (%)	n (%)	n (%)
RBC	n (%)	n (%)	n (%)
Hemoglobin	n (%)	n (%)	n (%)
Hematocrit	n (%)	n (%)	n (%)
Platelets	n (%)	n (%)	n (%)
Neutrophils (segs)	n (%)	n (%)	n (%)
Neutrophils (bands)	n (%)	n (%)	n (%)
Lymphocytes	n (%)	n (%)	n (%)
Monocytes	n (%)	n (%)	n (%)
Eosinophils	n (%)	n (%)	n (%)
Basophils	n (%)	n (%)	n (%)

path\t_program.sas date time

Table 6.1
Day of Maximal ICDRG Score
Evaluable Population

Day of ICDRG Maximal Severity Score	Treatment Regimen 2 (N=)	
	rHuPH20	Placebo
Never had an ICDRG Score More Severe than Day 3	n (%)	n (%)
Day 4	n (%)	n (%)
Day 5	n (%)	n (%)
Day 6	n (%)	n (%)
Day 7	n (%)	n (%)
Day 14	n (%)	n (%)

Note: For both injection types (rHuPH20 and Placebo), each subject will contribute one result based on the single most severe patch assessment reported.
path\t_program.sas date time

Programmer Note: Table 6.2 will contain the same information for the ITT population.

Table
Treatment Emergent Adverse Events by System Organ Class
Safety Population

System Organ Class / Preferred Term	Safety Population (N=)	
	Number of Subjects [1]	Number of Events
Subjects Reporting at Least One Adverse Event	n (%)	n
System Organ Class 1	n (%)	n
Preferred Term 1	n (%)	n
Preferred Term 2	n (%)	n
.		
System Organ Class 2	n (%)	n
Preferred Term 1	n (%)	n
Preferred Term 2	n (%)	n

[1] At each level of summation (overall, system organ class, preferred term), subjects reporting more than one adverse event are counted only once.
path\t_program.sas date time

Table
Treatment Emergent Adverse Events by System Organ Class and Severity
Safety Population

System Organ Class / Preferred Term [1]	Safety Population (N=)				
	Mild	Moderate	Severe	Life Threatening	Fatal

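### The only grade-change count in the SAP is a fall of at least 1 grade: rises have no table in Regimen 1, and in Regimen 2 a stronger Day 3 reaction becomes the baseline

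*SAP*

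**What the plan says.** SAP 8.1 makes the ICDRG grade (0, 1/2, 1, 2 or 3) on Days 3 to 7 and 14 the primary variable. SAP 8.2 then defines the secondary variables only through reductions of at least 1 grade in at least one patch region: after treatment in both regimens, and at 48 hours in Regimen 2. SAP 9.1 leaves the evaluation to a qualitative medical review of the scores. The review has two items. One is a possible treatment effect, with no direction stated. The other is "Proportion of subjects that have a ≥ 1 grade reduction in at least one patch region".

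SAP 8.4 sets Day 3 as the grade baseline for both regimens. In Regimen 2 the first injection is on Day 1, so this baseline is read after drug exposure.

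The table list in SAP Appendix A contains one ICDRG table, Table 6. It covers Regimen 2 only, gives the day of the maximal score by injection type, and shows no grade. Its first row is "Never had an ICDRG Score More Severe than Day 3". SAP 9.1 sends a subject there when the maximum came before the treatment injections.

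The protocol (section 8) states "The alternative hypothesis is that rHuPH20 will be better than placebo control". The SAP (section 9) gives the null as "The null hypothesis is that rHuPH20 will not be different than what will be observed from placebo control" and adds "No formal statistical comparisons between treatments are planned".

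**The concern.** This is a proof-of-concept study in dermatitis, and safety and tolerability are among its primary objectives. A reader of the report will want to know how often sites got better and how often they got worse, by injection type. The only change count that the SAP names answers the first question and says nothing on the second.

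The Day 3 reading in Regimen 2 matters most. The first study hypothesis is that pre-treatment lessens the reaction, and Day 3 is where that would first show. Yet no table gives Day 3 grades by injection type, and the baseline rule turns a stronger Day 3 reaction into room for a later improvement.

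**Working it through.** **The plan's own figure.** SAP 11 says "The sample size of 20 evaluable subjects is intended to provide a sufficient sample size", with no alpha, power, effect size or variance. There is nothing to reproduce; 20 is used below only as a denominator.

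**Inputs from the documents.** Grade scale (SAP 8.1). Day 3 baseline (SAP 8.4). Two rHuPH20 sites of four per regimen: Protocol 3.1 says "two random patch areas in Treatment Regimen 1 will be assigned rHuPH20" and applies the same concept to Regimen 2. Scores on Days 3 to 7 and 14 give 8 sites × 6 days = 48 readings per subject, or 48 × 20 = 960 in all.

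**Assumption.** The responder count is made separately for rHuPH20 and placebo sites within each regimen. SAP 8.2 does not say so, but SAP 9.1 shows scores by injection type.

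**Step 1: what the rule can see.** Five graded scores give 5 × 5 = 25 pairs of baseline and later score:

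| Change from Day 3 | Pairs | Counted? |
|---|---|---|
| Fall of at least 1 grade | 8 | yes |
| Fall of half a grade | 2 | no |
| No change | 5 | no |
| Rise of half a grade | 2 | no |
| Rise of at least 1 grade | 8 | no |

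The eight pairs with a rise of at least 1 grade share a category with no change.

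**Step 2: size, on assumed rates.** The documents give no rates. At one later reading, let each site fall by at least 1 grade with probability p and rise by at least 1 grade with probability q. For two independent rHuPH20 sites:

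- responder share = 1 − (1 − p)²
- share with any worse site = 1 − (1 − q)²
- share counted as responder while the other site is worse = 2pq

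With p = 0.3, responders = 1 − 0.7² = 51.0% (10.2 of 20) at every q. The share with any worse site is 0% at q = 0, 1 − 0.8² = 36% (7.2 of 20) at q = 0.2, and 1 − 0.6² = 64% (12.8 of 20) at q = 0.4.

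| p | Responders, any q | Responder with other site worse, at q = 0 / 0.2 / 0.4 |
|---|---|---|
| 0.1 | 19.0% | 0% / 4% / 8% |
| 0.3 | 51.0% | 0% / 12% / 24% |
| 0.5 | 75.0% | 0% / 20% / 40% |

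If a subject's two sites always moved together, the responder share would be p, the share with a worse site q, and masking 0. The responder share would still not move with q.

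**Step 3: Regimen 2 at Day 3.** Take a hypothetical subject with both rHuPH20 sites at +++ and both placebo sites at ++ on Day 3, and all four at ++ from Day 4 on. The rHuPH20 change is 2 − 3 = −1, a counted reduction. The placebo change is 2 − 2 = 0, not counted. Both maxima were reached on Day 3, so Table 6 puts both injection types in its first row. The summaries favour rHuPH20, although its sites never scored below placebo and scored one grade above it on Day 3. The Figure 1 layout happens to show the same sequence, +++ on Day 3 and ++ on Day 4, at a placebo site. That is placeholder content, not evidence.

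**Step 4: Table 6 after Day 3.** Each subject contributes one result per injection type, from the most severe patch, dated to the first time the maximum is reached. If one rHuPH20 site is ++ on Day 3 and the other goes from + to ++ on Day 4, the maximum dates to Day 3 and the rise is not counted.

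**The case against.** A reader might infer that the plan counts only falls, or reports only benefit. The documents do not support that. The primary variable is the grade itself, the first item of the medical review has no direction, and Figure 1 and Listing 8 show every score by subject, site, day and injection type. Listing 8 also marks the maximal score for each injection type. A Regimen 2 subject who goes above the Day 3 maximum leaves the first row of Table 6. TEWL and chromometer readings are plotted by site against a Day 1 baseline and can move either way. Injection-site reactions must be recorded as adverse events (Protocol 5.3.17), and Table 12 splits adverse events by regimen and injection type. All of this stands. It does not supply a count: the individual displays leave 960 readings to qualitative review, and an adverse-event table at sites already inflamed by nickel is not a tally of grade change.

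A reader might also infer that the labelled action makes worsening plausible. Protocol 1.1 describes the approved product as "an adjuvant to increase absorption and dispersion of other injected drugs". Nickel is applied by patch, not injected, and in Regimen 1 the patches come off before the first injection. In Regimen 2 the patch goes over the injection site after 10 minutes, so the thought is more natural there. But no section says that rHuPH20 could aggravate a nickel reaction, and Protocol 1.3 expects the opposite. The gap in the summaries does not depend on a mechanism.

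Finally, a no-difference null with an alternative of better leaves worse uncovered. That is true as logic but changes no planned output, because no test is planned. Direction would matter only if one were added: with 15 of 20 subjects worse, an exact sign test gives p = 0.994 one-sided for better and 0.041 two-sided.

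**Conclusion.** The gap is real and limited. The only named grade-change count cannot separate worsening from no change, and it lets one improved site outweigh a worse one. Regimen 1 has no tabulated count of rises. In Regimen 2 a stronger reaction already present at Day 3 is taken into the baseline and can later be credited as a reduction.

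The size is illustrative: a constant 51% responder share against 0% to 64% of subjects with a worse site rests on assumed rates, two independent sites and one later reading. The insensitivity to rises follows from the rule itself; the amount of masking depends on how closely a subject's two sites move together.

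The raw scores are shown in full and the study is a descriptive pilot, so nothing is lost beyond recovery. The change is still worth making: SAP 9.1 calls the primary analysis a pair-wise intra-subject comparison, and section 8 of the protocol promises dermatitis scores summarized by treatment group. No planned ICDRG table delivers either for the grades.

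**What to change.** Add to SAP 9.1 and Appendix B one descriptive table by regimen, day (4, 5, 6, 7 and 14) and injection type:

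- the number of sites and of subjects with a rise of at least 1 grade from Day 3, no such change, and a fall of at least 1 grade. A subject with sites in both directions counts in both rows, and a footnote should say so;
- the number of sites and of subjects with any +++ score;
- the number of sites with no grade (irritant or missing).

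For Regimen 2 at Day 3, add the grade distribution by injection type and the number of subjects whose mean rHuPH20 grade is higher than, equal to, or lower than their mean placebo grade. This also gives the 48-hour endpoint a defined comparator; against the Day 3 baseline its change is zero by construction.

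Restating the alternative as a difference in either direction is optional.

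The cost is one table from data already collected, and a result that may look less favourable. Make the change before database lock and unblinding, since SAP 4 treats analyses after unblinding as post hoc.

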## 2. STUDY OBJECTIVES

### 2.1. Primary Objective

- Determine the treatment effect of rHuPH20 or placebo control injection on the exposure to topical nickel allergen (Treatment Regimens 1 and 2)
- Determine the time to onset and severity of the cutaneous reaction to nickel allergen after pre-treatment with rHuPH20 or placebo control (Treatment Regimen 2)
- Assess the safety and tolerability of the rHuPH20 injection

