##### **Treatment Regimen 2:**

This regimen will assess the prevention and treatment of contact allergy to nickel sulfate. Each subject will receive in the center of each lower space on the back, either an ID syringe push bolus injection of rHuPH20 or placebo control. Exactly 10 minutes after the injection, a single

row of four patches (1, 2.5, or 5% nickel sulfate patches; determined for each subject during the Screening period) will be placed over the center of the ID injection. After 48 hours, the patches will be removed and an assessment will be made of the reaction site as per the ICDRG scoring system. The subject will receive an ID injection of the same study drug from pre-treatment in the center of the cutaneous reaction once daily for 5 days. Subjects will be evaluated for efficacy, safety, and tolerability, on a daily basis. A final evaluation will be conducted 7 days after the last dose of study treatment.

Each of the injections will consist of 0.25 mL of rHuPH20 (3,000 U) or 0.25 mL of placebo control.

Safety, tolerability, and efficacy will be assessed through physical examinations, signs and symptoms at injection sites, vital signs, and adverse events.

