#### Nickel Sulfate and Vehicle Control Patches

Follow the instructions in [Appendix C](#). Follow the manufacturer's instructions for filling the unit chambers. Concentrations of 1%, 2.5% and 5% nickel sulfate solution will be used to determine the subject's allergic reaction to nickel. Apply the test patches to a clean surface on the upper back (at least 2 cm above the area to be used for the post-screening visits). Have the subject return to the study site after 48 hours to have the test results interpreted.

The concentration of nickel sulfate that causes no greater than + + cutaneous reaction (International Contact Dermatitis Research Group [ICDRG] scoring scale, see [Appendix B](#)) will be the assigned dose for use per subject for the study. One half (50%) of study subjects will

be treated using the nickel concentration that elicits a + cutaneous reaction and the other half (50%) of study subjects will be treated with the nickel concentration that elicits a ++ cutaneous reaction. Any subjects not meeting the cutaneous reaction scale will be a screen failure.

Record the nickel sulfate concentration to be used for the subject in the subject's source documentation.

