2. OBJECTIVES

The primary objectives of the study are:

- Determine the treatment effect of rHuPH20 or placebo control injection on the exposure to topical nickel allergen (Treatment Regimens 1 and 2)
- Determine the time to onset and severity of cutaneous reaction to nickel allergen after pre-treatment with rHuPH20 or placebo control (Treatment Regimen 2)
- Assess the safety and tolerability of the rHuPH20 injection

Secondary objectives include:

- Proportion (%) of subjects who, with pre-treatment, have a ≥ 1 grade reduction of the cutaneous reaction to nickel sulfate in at least one patch region at 48 hours
- Proportion (%) of subjects with a ≥ 1 grade reduction of the cutaneous reaction to nickel sulfate in at least one patch region after treatment
- Proportion (%) of subjects that have a ≥ 1 grade reduction of the cutaneous reaction to nickel sulfate in at least one patch region at Days 4, 5, 6, 7 and 14.
- Safety and tolerability of the injection based on AEs, physical examinations, and vital signs

Descriptive-Only parameters include:

- Chromometer readings of the allergen test sites on Day 1, Day 3 (48 hrs), Day 4 (72 hrs) and Day 5 (96 hrs) after the placement of the patches
- TEWL (Trans-epidermal water loss) assessment on Day 1, Day 3 (48 hrs), Day 4 (72 hrs) and Day 5 (96 hrs) after the placement of the patches

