8.1 Primary Variables

The primary efficacy endpoint will be based on the International Contact Dermatitis Research Group (ICDRG) Scoring Scale. Using the ICDRG Scoring Scale, each score will be assigned a Sponsor-defined “grade”. Scores with stronger reactions will be assigned grades with higher values with a maximum grade of 3; scores with weaker reactions will receive lower values with a minimum grade of 0. Grade assignments based on the ICDRG Scoring Scale are shown in the table below.

International Contact Dermatitis Research Group (ICDRG) Scoring Scale

Grade	Score	Interpretation
0	-	Negative reaction
1/2	?	Doubtful reaction; faint macular erythema only
1	+	Weak (nonvesicular) positive reaction; erythema, infiltration, papules, vesicles
2	++	Strong (vesicular) positive reaction; erythema, infiltration, papules, vesicles
3	+++	Extreme positive reaction; bullous reaction
NA	IR	Irritant reaction of different types

Treatment effect of rHuPH20 or placebo control injection on the exposure to topical nickel allergen will be assessed using ICDRG grades for Treatment Regimens 1 and 2 at Day 3 through Day 7 and Day 14.

Regimen 2 only: For each subject, the day of maximal ICDRG score will be determined for each injection type (rHuPH20 and Placebo). The maximal ICDRG score will be the highest score reported for each subject. If the maximal ICDRG score for a particular subject is reported more than one time, the first instance will be used to determine the day when the maximal ICDRG score was reached.

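### Table 6 uses day of maximal ICDRG score as the onset measure for pre-treatment, but a day of maximum is not an onset and every dated row follows re-injection, so it cannot isolate the pre-treatment effect

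*SAP*

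**What the plan says.** The second primary objective (Protocol 2.1, repeated in SAP 2) is to "Determine the time to onset and severity of the cutaneous reaction to nickel allergen after pre-treatment", and it applies to Regimen 2 only. Protocol 8 and SAP 9 state the pre-treatment hypothesis separately from the treatment hypothesis.

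In Regimen 2 each site is injected on Day 1, patched 10 minutes later and read at patch removal 48 hours on (Day 3). After that, "The subject will receive an ID injection of the same study drug from pre-treatment in the center of the cutaneous reaction" once daily for five days. Protocol 3.2 places those doses on Days 3 to 7.

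For onset, SAP 9.1 says "the day of maximal ICDRG Score will be used to assess the possible effect each injection type has on the onset of reaction". The possible days are "the following: Day 4, Day 5, Day 6, Day 7, and Day 14". If the maximum occurred before treatment, "the subject will be reported as never having had an ICDRG Score more severe than Day 3 for summary purposes". For ties, SAP 8.1 says "the first instance will be used to determine the day when the maximal ICDRG score was reached". The Table 6 layout covers Regimen 2 only and takes one result per subject per injection type, from the worst patch.

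**The concern.** The objective asks when the reaction starts after a pre-treatment injection. The table reports when the score is highest during a course of further injections of the same drug. If the distribution of peak day differs between rHuPH20 and placebo sites, the cause could be the Day 1 injection, the Day 3 to 7 injections, or both. A reader who takes Table 6 as the answer to the onset objective could credit pre-treatment with an effect of treatment. A real pre-treatment effect visible at 48 hours could also be missed, because nothing in the planned tables summarises it. Table 6 is the only efficacy table in the SAP's list of tables, so it is likely to carry weight in the study report.

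**Working it through.** The plan gives no figure to reproduce: no alpha, power or effect size is stated, and no formal comparison is planned. The check uses the injection schedule and the Table 6 rule.

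**Step 1. Injections before each reading.** Inputs: doses on Days 3 to 7 (Protocol 3.2); the Day 3 score is taken at patch removal, before the first treatment dose; the Listing 15 layout puts the ICDRG score in the pre-injection examination. The count for a reading on Day d is the number of dosing days in {3, 4, 5, 6, 7} that are earlier than d.

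| Reading | Pre-treatment injections | Treatment-phase injections | Place in Table 6 |
|---|---|---|---|
| Day 3 | 1 | 0 | no dated row; a Day 3 maximum goes to the Never row |
| Day 4 | 1 | 1 | Day 4 |
| Day 5 | 1 | 2 | Day 5 |
| Day 6 | 1 | 3 | Day 6 |
| Day 7 | 1 | 4 | Day 7 |
| Day 14 | 1 | 5 | Day 14 |

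No dated row reflects pre-treatment alone.

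**Step 2. Maximum against onset.** Under Protocol 5.1.1 the assigned nickel concentration is one that gave + or ++ at screening, where the instruction is "Have the subject return to the study site after 48 hours to have the test results interpreted". At placebo sites a reaction is therefore expected by the first study reading, also at 48 hours. There is no reading between Day 1 and Day 3, so such an onset is known only to lie somewhere in the first 48 hours. A site at + on Day 3 that reaches ++ on Day 6 is reported as Day 6, although its reaction had started by Day 3.

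**Step 3. What the Never row contains.** Apply the first-instance rule to constructed grade sequences for Days 3, 4, 5, 6, 7 and 14:

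| Pattern | Grades | Row |
|---|---|---|
| Early strong peak | 2, 2, 1, 1, 1/2, 0 | Never |
| Complete prevention | 0, 0, 0, 0, 0, 0 | Never |
| Weaker reaction throughout | 1, 1, 0, 0, 0, 0 | Never |
| Delayed peak, then suppressed by treatment | 1/2, 1/2, 1/2, 0, 0, 0 | Never |
| Peak delayed by pre-treatment, treatment inert | 1, 2, 1, 1, 1/2, 0 | Day 4 |
| Pre-treatment inert, flare after the Day 3 injection | 1, 2, 1, 1, 1/2, 0 | Day 4 |

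The first four patterns are clinically different and share one row. The last two have different causes and identical scores. Leaving the Never row requires a later score above the Day 3 score, so membership depends on readings after re-injection.

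**Step 4. Illustration under assumed values.** None of these inputs is in the documents: 200,000 simulated subjects, two sites per injection type, a bell-shaped reaction curve (width 2.2 days) peaking on average 2.7 days after patching (SD 0.7), mean height 2.0 (SD 0.5), noise SD 0.25, cut into the SAP grades.

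| Scenario | Never row | Mean worst-site Day 3 grade |
|---|---|---|
| Placebo | 77.4% | 2.13 |
| Pre-treatment delays the peak by 0.6 day | 59.0% | 1.95 |
| Treatment lowers later scores by 0.3 | 90.8% | 2.13 |
| Both | 77.9% | 1.95 |
| Treatment flare of 0.2 only | 64.1% | 2.13 |
| Pre-treatment lowers height by 0.5 | 75.8% | 1.67 |

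Across these scenarios the Never row runs from 59.0% to 90.8%. Two real effects can cancel in it, and a flare from treatment moves it the same way as a pre-treatment delay. The Day 3 grade responds to pre-treatment only.

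**Step 5. The 48-hour endpoint.** SAP 8.2 asks for a reduction of at least one grade at Day 3 in Regimen 2. SAP 8.4 sets each region's baseline at Day 3. Change = Day 3 grade minus Day 3 grade = 0 at every site, so the proportion is 0% for both injection types.

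**The case against.** A reader might infer that the whole objective is judged only from Day 4 on. The documents do not support that. SAP 8.1 lists grades from Day 3, and Figure 1 and Listing 8 show Day 3 scores at every Regimen 2 site with the injection type marked. The severity half therefore has its Day 3 data on display, though SAP 9.1 gives those scores only a qualitative medical review and no summary.

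Nor is Day 3 absent from Table 6. A Day 3 maximum is counted in the Never row, and a pure delay would move subjects out of that row. This stands, but the row cannot say why they moved.

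It would also be wrong to say that nothing targets pre-treatment at 48 hours. SAP 8.2 has such an endpoint; the Day 3 baseline disables it.

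Regimen 1 supplies treatment-only sites in the same subject, with the same nickel concentration and the same Day 3 to 7 schedule. This is a partial handle on the treatment effect, but Table 6 has no Regimen 1 column and no cross-regimen summary is planned.

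Finally, SAP 9.1 speaks of a possible effect of each injection type and does not name pre-treatment. Regimen 2 is openly a prevention-and-treatment regimen, and the pilot is descriptive. All of that stands. rHuPH20 against placebo remains a fair randomised contrast of the combined regimen, provided it is labelled as such.

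**Conclusion.** The point holds for the onset half of the second primary objective and for Table 6.1/6.2. Day of maximum is not onset. All five dated rows carry 1 to 5 treatment-phase injections on top of the single pre-treatment injection, and the Never row mixes opposite outcomes. Table 6 therefore cannot isolate the pre-treatment effect, while the one reading that can, Day 3, is displayed but not summarised.

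The stronger readings, that Day 3 is ignored or that the objective has no pre-treatment data, are not supported. The defect is a mislabelled measure and a missing summary; the data to repair it are collected.

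The conclusion rests on the injection schedule and the Table 6 rule. The injection counts assume that the Day 4 to 7 scores precede that day's dose, as the Listing 15 layout indicates; a later reading would add one injection to each of those days and change nothing. The expectation of a placebo-site reaction by 48 hours assumes that the study patches behave as the screening patches did. The simulated percentages are illustrative only.

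**What to change.** In SAP 8.1 and 9.1:

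- Add a table of the Day 3 ICDRG grade at Regimen 2 sites, rHuPH20 against placebo paired within subject, as the readout for the second primary objective. Show the grade distribution and grade 1 or higher (yes or no), and state how the two sites per injection type are combined.
- State that onset before 48 hours is not observed.
- Keep Table 6, but describe it as day of maximal reaction and not as onset.
- Label Table 6 and all Regimen 2 results from Day 4 on as the combined effect of pre-treatment plus treatment.
- If first visit at grade 1 or higher is also tabulated, give its Day 4 to 14 entries the same label. From Day 4 it is confounded in the same way, so it cannot serve as a clean onset measure for pre-treatment.

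The cost is SAP wording and one more table from scores already collected, with no change to visits or dosing. The onset claim narrows to whether a reaction is present by 48 hours.
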